3.4 Fostamatinib Safety and Pharmacokinetics

3.4.1 Single Ascending Dose Safety and Pharmacokinetics

R406, the major metabolite generated through the dephosphorylation of the prodrug R788 by intestinal phosphatases, appears rapidly in the systemic circulation after fostamatinib dosing, with median t_{max} ranging between 1 and 3 hours. Negligible levels of R788 are found in plasma. The terminal half-life of R406 ranges from 12 to 19 hours. Increasing the dose of fostamatinib tablets from 100 to 300 mg results in approximately dose-proportional increases in R406 exposure.

The geometric mean absolute bioavailability of R406 was estimated to be 54.6% (90% CI: 42.5 to 70.3%) in a bioavailability study in which 10 healthy volunteers were given a single oral dose of 150 mg fostamatinib and a 100 mcg intravenous (IV) dose of radiolabeled R406. Following the IV dose of R406 the volume of distribution at steady state (V_{ss}) was determined to be 256 L and total clearance (CL) of R406 was determined to be 15.7 L/h.

In healthy Japanese subjects, mean area under the curve (AUC) and maximum plasma concentration (C_{max}) were approximately dose-proportional between 50 and 200 mg single-doses. Following single-dose administration of fostamatinib 150 mg, higher C_{max} (~45% higher) and AUC (~27% higher) values were observed in Japanese subjects compared with white subjects (of European ethnicity), however, exposure in Japanese subjects generally tended to be comparable to other studies in which white subjects were enrolled.

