3.6 Safety

A number of Phase 2 and 3 studies of fostamatinib have been conducted in several indications including ITP, RA and B- and T-cell lymphomas. Doses of fostamatinib have ranged from 50 to 250 mg PO *bid*, depending on the indication being treated. The majority of patients have been treated at doses ranging from 50-150 mg PO *bid*.

The overall pattern of adverse effects of fostamatinib in these various clinical settings (patients

with RA, severely ill patients with lymphoma and advanced solid tumors, chronically ill patients with ITP, and in healthy subjects), has been consistent, and includes dose-dependent effects on blood pressure (BP), ANC, dizziness, gastrointestinal (GI) complaints and liver function test abnormalities, all of which are reversible and manageable with appropriate safety monitoring (Table 1). The ITP patients (on no anti-metabolites or chemotherapy) have not manifested neutropenia, despite receiving higher doses of fostamatinib than the RA patients. The lymphoma patients have experienced more cytopenias, and infections, consistent with their extensive pre-treatment and underlying disease. In patients with solid tumors, the overall pattern of reported AEs was consistent with a population of heavily pretreated, relapsed patients with solid tumors of varying histologies.

**Table 1: Frequent Adverse Events
(Pooled Data - Phase 3 Placebo-Controlled RA Studies)**

Sign/Symptom	Fostamatinib		Placebo N = 715 254 PY
	100 mg bid N = 723 288 PY	100 mg bid (1 month) followed by 150 mg qd N = 710 277 PY	
BP > 140/90	333 (46%)	315 (44%)	170 (24%)
BP > 160/100	66 (9%)	63 (9%)	24 (3%)
Diarrhea	94 (33%)	112 (40%)	32 (13%)
Nausea	36 (13%)	41 (15%)	17 (7%)
Dizziness	18 (6%)	12 (4%)	5 (1%)
Abdominal Pain*	39 (14%)	38 (14%)	27 (11%)
ALT/AST \geq 3 x ULN	38 (5%)	37 (5%)	17 (2%)
PMN < 1500/ μ L	66 (9%)	41 (6%)	8 (1%)

ALT= Alanine aminotransferase, AST = Aspartate aminotransferase, BP = Blood pressure, PY = Patient years, PMN = Polymorphonuclear leukocytes, ULN = Upper limit of normal

* Represents various verbatim terms

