3.6.3 Neutropenia

Dose-dependent decreases in ANC have been observed in the majority of studies with fostamatinib. Transient neutropenia (typically resolving within 5 to 7 days of discontinuation of fostamatinib) has been observed in RA patients receiving fostamatinib at doses ranging from 50 to 150 mg *bid*. Neutropenia was not observed to any significant degree in the Phase 2 ITP trial (although the experience was admittedly limited). Dose reduction has generally resulted in resolution of the neutropenia and permitted patients to remain on study drug for prolonged periods. To date, in the RA studies, there is no clear association between neutropenia and an increased risk of infection, and no evidence that treatment with fostamatinib increases the risk of opportunistic infection.

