**Table 1: Schedule of Study Procedures**

	Day 1 Screen/ Enrollmenta	End of Month 1 (± 3 days)	Months 2–18 (± 3 days)	Months 19– 60 (± 1 week)	Follow-up (± 7 days)i
Informed consent	X				
Inclusion/Exclusion	X				
Physical exam/KPS	X	X	monthly	every other month	X
Concomitant medications	X	X	monthly	every other month	X
Vital signs b	X	X	monthly	every other month	X
Bleeding assessment c	X	X	monthly	every other month	X
ECG	X				
Hematology d	X		monthly	every other month	X
Platelets	X	X	monthly	every other month	X
Serum chemistries (including LFTs) e	X		Months 4, 8, 12, 16	every other month	X
LFTs only f			monthly (in months full serum chemistries not done)		X
Immunoglobulin levels	X				X
Urinalysis	X		Months 4, 8, 12, 16	every 4 months	X
Urine pregnancy test g	X		every other month	every other month	
SF-36 h	X		Month 12		
AEs	X	X	monthly	every other month	X
PK			Month 2		
Study drug dispensed/Accountability	X	X	monthly	every other month	
Dose adjustment (prn)	X	X	monthly	every other month	

- a. **Screen/Enrollment (Day 1):** These procedures are equivalent to Week 24 visit of Study C-935788-047 or C-935788-048; assessments performed as part of Week 24 may be used to assess subject's eligibility to roll over and do not need to be repeated specific to Study C-935788-049.
- b. **Vital Signs:** blood pressure, pulse and temperature
- c. **Bleeding assessment:** IBLS scale only; prior to Version 4, protocol used both IBLS and WHO bleeding scales
- d. **Hematology:** CBC with differential, RBC, hemoglobin, hematocrit, MCHC, MCH, MCV, MPV, RDW, reticulocytes
- e. **Serum chemistries:** Na, K, Cl, bicarbonate (CO2), Ca, PO4, BUN, creatinine, globulin, glucose, LDH, AST, ALT, alkaline phosphatase, total bilirubin, total protein, albumin
- f. **LFTs:** ALT, AST, ALP, LDH, and bilirubin (total and direct)
- g. **Pregnancy Test:** For women of childbearing potential, regardless of birth control methodology
- h. **SF-36:** At visits where the SF-36 is evaluated the SF-36 must be the first assessment performed.
- i. **Follow-up visit:** to be completed approximately 2 weeks (+/- 7 days) after subject's last treatment or at the time of early treatment termination.

[figure not shown]

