## 11.2 Clinical Laboratory Tests

Descriptive statistics will be presented by scheduled visit for the actual values and the changes and percentage changes from baseline for each selected quantitative laboratory test (hematology, serum chemistry, and liver function test). Actual values of categorical urinalysis test results will be summarized by scheduled visit. Lab values that are out of normal range will be flagged in the data listings.

Box plots indicating mean and median as well as the 25th and 75th percentiles, reference plots, and spaghetti plots will be presented by study scheduled visit for both raw values and changes from baseline.

Descriptive statistics for the actual values, changes from baseline, and maximum value observed post baseline will be presented by scheduled visit in the present study. In addition, two types of shift tables based on lab values classified per Common Terminology Criteria for Adverse Events (CTCAE) Grade Version 5.0 will be provided as follows:

- Grades based on baseline lab values vs. the grades based on the worst post-baseline lab values observed in the present study,
- Grades based on baseline lab values vs. the grades based on the last post-baseline lab value observed in the present study.

These two types of shift table summaries above will be applied to the following selected lab parameters, respectively:

- Liver function tests (i.e., ALT, AST, total bilirubin and indirect bilirubin)
- Absolute neutrophil count (ANC)
- Alkaline Phosphatase

Regarding lab values of ALT, the following additional analyses will be performed:

- Descriptive statistics for the average number of events of lab value increasing from baseline for each patient.

- Frequencies and percentages for number of patients with the events of lab value increasing from baseline

Same additional analyses will be performed for AST.

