### 11.3 Vital Signs

Descriptive statistics will be presented by scheduled visit for the actual values and the changes and percentage changes from baseline for each vital sign. The maximum post baseline systolic blood pressure categories ( $< 140$  mmHg,  $140 - < 160$  mmHg,  $160 - < 180$  mmHg and  $\geq 180$  mmHg) will be summarized using counts and percentages. This analysis will also be performed by baseline use of anti-hypertensives (yes/no). The anti-hypertensives are the medications with any of the following ATC codes at baseline: C02 (anti-hypertensives), C03 (diuretics), C04 (peripheral vasodilators), C07 (beta blocking agents), C08 (calcium channel blockers), and C09 (agents acting on the rennin-angiotensin system). These analyses will be repeated for maximum post baseline diastolic blood pressure categories ( $< 90$  mmHg,  $90 - < 100$  mmHg,  $100 - < 110$  mmHg and  $\geq 110$  mmHg).

The number and percentage of following types of patients will be presented:

- Patients with systolic BP  $\geq 140$  mmHg or diastolic BP  $\geq 90$  mmHg at consecutive visits (2 or more visits, 3 or more visits) of present study
- Patients with systolic BP  $\geq 140$  mmHg or diastolic BP  $\geq 90$  mmHg anytime during the post-baseline of present study
- Patients with systolic BP  $\geq 160$  mmHg or diastolic BP  $\geq 100$  mmHg at consecutive visits (2 or more visits, 3 or more visits) of present study
- Patients with systolic BP  $\geq 160$  mmHg or diastolic BP  $\geq 100$  mmHg anytime during the post-baseline of present study
- Patients with systolic BP  $\geq 180$  mmHg or diastolic BP  $\geq 110$  mmHg at consecutive visits (2 or more visits, 3 or more visits) of present study
- Patients with systolic BP  $\geq 180$  mmHg or diastolic BP  $\geq 110$  mmHg anytime during the post-baseline of present study

In addition, shifts based on new guidance in blood pressure (**Appendix 14.3**) from normal, elevated, Stage 1, Stage 2 and hypertensive crisis at baseline to normal, elevated, Stage 1, Stage 2 and hypertensive crisis for the maximum observed value, and the last value post baseline will

be tabulated. The maximum observed blood pressure and the last blood pressure post baseline will be based on both scheduled and unscheduled visits.

Box plots indicating mean and median as well as the 25th and 75th percentiles, reference plots, and spaghetti plots will be presented by scheduled visit for both raw values and changes from baseline.

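### The last-value shift tables for laboratory grades and blood pressure have no on-treatment limit, so they mix on-drug values with Follow-up values taken 7 to 21 days off drug

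*SAP*

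**What the plan says.** SAP 11.2 defines two CTCAE shift tables for ALT, AST, total and indirect bilirubin, ANC and alkaline phosphatase. One is "Grades based on baseline lab values vs. the grades based on the worst post-baseline lab values observed in the present study". The other, at issue here, is "Grades based on baseline lab values vs. the grades based on the last post-baseline lab value observed in the present study".

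SAP 11.3 plans shifts in blood-pressure category from baseline to the maximum and to the last post-baseline reading, and adds: "The maximum observed blood pressure and the last blood pressure post baseline will be based on both scheduled and unscheduled visits". Neither section limits the last value to time on treatment or says how Follow-up is handled.

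The schedule (SAP Table 1, same in Protocol Table 2) marks vital signs, hematology, serum chemistries and LFTs at Follow-up. Footnote i times that visit as "to be completed approximately 2 weeks (+/- 7 days) after subject's last treatment or at the time of early treatment termination". Protocol 7.5 gives only the 2-week timing. Protocol 7.9 gives withdrawn subjects a visit with the same assessments and states no washout interval. Under Protocol Appendix 10, patients who continue on drug after final lock have no final visit.

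On reversibility, Protocol 3.6 lists effects that include blood pressure, ANC and liver tests and calls them "all of which are reversible and manageable with appropriate safety monitoring". Protocol 3.6.3 describes neutropenia in rheumatoid arthritis (RA) patients as "typically resolving within 5 to 7 days of discontinuation of fostamatinib". Protocol 3.4.1 states: "The terminal half-life of R406 ranges from 12 to 19 hours".

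**The concern.** Long-term safety is the primary objective. Of the planned shift tables, the last-value tables are the ones that could show where patients stood when treatment ended, because the worst-value tables cannot. As defined, they do not answer that question cleanly. A patient seen 2 weeks after the last dose contributes a washed-out value. A patient assessed at early termination, or still on drug at lock, contributes an on-drug value. The proportions depend on how each patient left the study, and that may itself be related to toxicity.

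A low count of abnormal last values could then mean that the drug was well tolerated at the end of treatment, or that abnormalities cleared after it was stopped. The table cannot separate the two.

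**Working it through.** The documents give no figure to reproduce here. The check has three parts.

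**1. Which measurement is the last value?** Read literally, it is the latest one in the study.

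| How the patient leaves | Source | Last value taken |
|---|---|---|
| Follow-up timed from the last dose | Footnote i; Protocol 7.5 | 14 ± 7 = 7 to 21 days off drug |
| Visit at early termination | Footnote i | about 0 days off drug |
| Withdrawal visit | Protocol 7.9 | interval not stated |
| Still on drug at final lock | Protocol Appendix 10 | latest on-drug visit |

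Protocol 7.6.6 adds to the mixture: clinically significant abnormal results are followed until they normalise or another cause is found. In a patient who interrupts and never restarts, the last value may be a recovery value even without a Follow-up visit.

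**2. How much drug is left at Follow-up?** Half-lives elapsed = hours off drug / half-life; fraction remaining = 2^-(half-lives). Half-life is 12 to 19 h (Protocol 3.4.1).

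- 7 days (168 h): 168/19 = 8.8 to 168/12 = 14 half-lives; 0.22% to 0.006% remaining.
- 14 days (336 h): 336/19 = 17.7 to 336/12 = 28 half-lives.
- 21 days (504 h): 504/19 = 26.5 to 504/12 = 42 half-lives.

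A visit timed from the last dose is therefore off drug in any practical sense. For ANC, the stated 5 to 7 day recovery is over by the earliest such visit, at day 7. The half-lives describe drug clearance only. The documents give no off-drug recovery time for transaminases, bilirubin or blood pressure, so no equivalent statement can be made for them.

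**3. What range could this produce?** Let N be patients, r the share abnormal at the last on-drug value, s the share of those whose last value comes from a visit 7 to 21 days off drug, and q the share of these recovered by then. The tabulated count is N × r × (1 − s × q). The documents give none of r, s or q for this trial. For illustration, take N = 150 (the enrolment cap) and r = 6% to 9%. These are the RA rates for neutrophils below 1500/µL on fostamatinib in Protocol Table 1, used as an assumed range only.

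- On-treatment count: 150 × 0.06 = 9.0 to 150 × 0.09 = 13.5.
- s = 0: 9.0 to 13.5, nothing lost.
- s = 0.5, q = 1: 4.5 to 6.75.
- s = 1, q = 1: 0.

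The value of r may be well below this range, because Protocol 3.6 and 3.6.3 report little or no neutropenia in ITP patients. The calculation shows only that the same on-treatment experience can give any count from all to none, depending on the visit mix.

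**The case against.** The strongest reply is that nothing is lost from the report. The worst-grade table covers the same laboratory parameters, and SAP 11.3 tabulates the maximum blood pressure beside the last. It also counts patients over each pressure threshold at any time and at consecutive visits. SAP 11.1 reports hypertension, neutropenia, transaminase elevation and bilirubin elevation as events of interest. This stands. A reader might infer that the plan hides toxicity, or that all toxicity present at the end of treatment is tabulated as recovered. The documents support neither: a low-ANC patient who recovers by Follow-up shows no shift in the last-value table but does show one in the worst-grade table.

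A reader might also take the half-life figures as proof that blood pressure and liver tests have normalised by Follow-up. That does not follow. Protocol 3.6.1 credits antihypertensive treatment with reducing the pressure effect, and a confirmed low ANC already leads to interruption under Protocol Appendix 2.

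By-visit summaries may also show Follow-up separately, since it is a scheduled column. That helps, but those summaries do not give an on-treatment categorical shift.

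It could be said that post-baseline was meant as on treatment, because SAP 5.7 equates the two. That wording covers only the maximum-pressure subgroup and sets no date rule. SAP 11.4, by contrast, limits the mean bleeding scores to a treatment period, so the SAP does write such limits where it wants them.

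Finally, the last value observed in the study can legitimately show persistence at study end, and no test or decision rule depends on it. That is fair, but the mixture of visit timings makes even persistence hard to read.

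**Conclusion.** The point holds in limited form. The two last-value shift tables have no on-treatment limit and combine on-drug values with values taken 7 to 21 days off drug, so they have no single interpretation. For some patients, toxicity present at the end of treatment may appear as no shift. The case is firmest for neutropenia and rests on the protocol's 5 to 7 day recovery in RA patients. For liver tests and blood pressure it rests only on the general statement of reversibility.

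The size cannot be computed. It depends on the unknown visit mix and recovery rates, and the illustrative ANC counts rest on borrowed RA rates. The effect is confined to these tables, but they bear on the primary objective and the correction is cheap, so it should be made before lock.

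**What to change.** In SAP 11.2 and 11.3, replace the single last-value shift with two columns:

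1. **Last on-treatment value.** Define it by a short window after the last fostamatinib dose, fixed before database lock and shorter than the stated 5 to 7 day recovery. Up to 3 days is one example; a prompt withdrawal visit would then still count. Flag values taken during a dose interruption.
2. **Off-treatment Follow-up value.** Use measurements after that window.

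Give the number of patients contributing to each column, since patients still on drug at lock have no off-treatment value. State whether unscheduled laboratory values count, as is already stated for blood pressure. Reconcile footnote i with Protocol 7.5 and 7.9 on the timing of the visit.

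The cost is SAP wording and one extra column per table. No new data are needed, because SAP 9.0 already analyses dosing duration and interruptions. There are two drawbacks. The on-treatment results may look less favourable. After Month 18, when visits are every other month, the last on-treatment value may be up to about two months old if no visit falls within the window. In return, the second column shows reversibility directly.

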7.1.2 Treatment Visits

The treatment period begins at the time of enrollment and may continue up to a total of 60 months. Over the course of the study, subjects will be expected to visit the clinic monthly for the first 18 months, followed by every 2 months for the remainder of the study. Assessments including platelet counts will be performed to evaluate the safety and efficacy of fostamatinib, and to determine if a dose adjustment is required. All visits are determined by the date of enrollment and should occur within the windows specified (refer to Table 2 for the complete schedule of study procedures).

[figure not shown]
Study drug accountability will be performed at each visit. New bottle of fostamatinib will be dispensed using the IWRS at each visit. Used bottles will be returned for accountability. At the final visit of the treatment period, final study drug accountability will be performed.

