7.3 Discontinuation of Nonresponders

After 3 months (12 weeks) of treatment, (and a minimum of 4 weeks treatment at 150 mg PO *bid*, unless this higher dose was not tolerated), any subject whose platelet count consistently

remains $< 50,000/\mu\text{L}$ should be discontinued from the study, unless tangible clinical benefit from the use of fostamatinib is evident and the Sponsor agrees (discuss any exceptions with the Sponsor's Medical Monitor). Examples of tangible clinical benefit may include, but are not limited to:

- Credible increase in platelet count (eg, increase in platelet count of at least $20,000/\mu\text{L}$ over the initial baseline to a count $\geq 30,000/\mu\text{L}$)
- Reduction in bleeding
- Reduction in the need for rescue therapy

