Appendix 1: Dose Modification for Possible Drug-Induced Liver Injury

The Investigator is responsible for determining whether the subject meets Hy's law criteria for severe liver injury; aspartate aminotransferase (AST) or alanine aminotransferase (ALT) $\geq 3x$ upper limit of normal (ULN) plus total bilirubin (TBL) $> 2x$ ULN and alkaline phosphatase (ALP) $< 2x$ ULN.

- **Note:** Fostamatinib is an inhibitor of UGT1A1, the enzyme responsible for the glucuronidation of bilirubin; occasionally an isolated increase in total and **unconjugated** (indirect) bilirubin may be observed. Study drug should not be interrupted for an isolated increase in total and unconjugated (indirect) bilirubin.
- The study Medical Monitor should be notified immediately of any potential case meeting Hy's law criteria.

Dose Adjustment

Starting Dose	Dose Level -1	Dose Level -2	Dose Level -3 ^a	Dose Level -4 ^a
100 mg PO bid	150 mg PO qd	100 mg PO qd	discontinue	----
150 mg PO bid	100 mg PO bid	150 mg PO qd	100 mg PO qd	discontinue

a The Sponsor's Medical Monitor should be consulted prior to consideration of dose modification to levels -3 or -4.

Identification

If AST or ALT $\geq 3x$ ULN and **total** bilirubin $> 2x$ ULN, with ALP $< 2x$ ULN (Hy's law criteria met), please follow the instructions below:

- Stop study drug treatment and **contact the Sponsor's medical monitor immediately to discuss the data and consider withdrawal** of the subject from the study for possible drug-induced liver injury.
- The Investigator will follow the subject until liver biochemistry parameters and any appropriate clinical symptoms and signs return to normal or baseline levels, or as long as medically indicated.
- The Investigator will investigate the etiology of the event and perform diagnostic investigations as discussed with the Sponsor's Medical Monitor.

If AST or ALT \geq 3x ULN **or** TBL $>$ 2x ULN, and the subject is exhibiting the following symptoms: nausea, vomiting, abdominal pain:

- Study drug administration should immediately be interrupted.
- LFTs, including bilirubin and alkaline phosphatase should be repeated every 3 days/72 hours until ALT/AST or TBL returns to $<$ 1.5x ULN.
- When the ALT/AST or TBL returns to $<$ 1.5x ULN study drug may be restarted at dose level -1.

If AST or ALT \geq 3x ULN **or** TBL $>$ 2x ULN and subject is asymptomatic:

- Repeat LFTs, including bilirubin and ALP, within 72 hours.

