### **5.8. Definition of Baseline Measurements**

For the summary of baseline characteristics of present study, the baseline characteristics used for summary are defined in **Section 4.1** and **4.2**.

For the calculation of change from baseline, the baseline value is defined as the last measurement for the corresponding variable prior to the first dose of fostamatinib in Study C-935788-047 or C-935788-048 (for fostamatinib patients in the previous study) or the present study (for placebo patients in the previous study).

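### SAP 11.2 leaves its additional ALT/AST event undefined, and no visible SAP table names the protocol's ULN multiples or counts ALT/AST and bilirubin elevation occurring together

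*SAP*

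**What the plan says.** SAP 11.2 lists two additional analyses for ALT and repeats them for AST. One is "Descriptive statistics for the average number of events of lab value increasing from baseline for each patient"; the other is "Frequencies and percentages for number of patients with the events of lab value increasing from baseline". Neither comes with a minimum rise, a ULN multiple, a grade or a confirmation rule. Under SAP 5.8, "the baseline value is defined as the last measurement for the corresponding variable prior to the first dose of fostamatinib", so each patient is compared with a single reading.

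These items are not the whole liver analysis. The same section plans CTCAE v5.0 shift tables, including "Grades based on baseline lab values vs. the grades based on the worst post-baseline lab values observed in the present study" and a last-value version, for ALT, AST, total and indirect bilirubin and alkaline phosphatase. It also plans by-visit summaries, maximum post-baseline values and flagged listings. SAP 4.5 and 11.1 add transaminase and bilirubin elevation as adverse events of interest.

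Protocol Appendix 1 works with explicit multiples: ALT or AST ≥3x ULN, ALT/AST above 5x ULN on repeat testing, and total bilirubin >2x ULN. It also has a combined criterion (ALT or AST ≥3x ULN, total bilirubin >2x ULN, ALP <2x ULN), for which "The Investigator is responsible for determining whether the subject meets Hy's law criteria for severe liver injury".

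**The concern.** Laboratory values vary from visit to visit. If any reading above one baseline reading is an event, most patients will have one by chance, and more so the longer they are followed. The study is open-label with no concurrent control, so there is no comparison rate against which to read a high percentage.

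The second issue is concurrency. Protocol 3.6.2 and Appendix 1 say that R406 inhibits UGT1A1 and that isolated rises in bilirubin can be expected. A bilirubin table alone therefore mixes this expected effect with possible injury, and only a joint count within patients separates them. Protocol 3.6.2 already reasons this way: of five earlier patients who met Hy's law criteria, one is set apart because bilirubin and transaminases were not raised at the same time. Long-term safety is the primary objective and liver function is a listed safety endpoint (Protocol 4.4).

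**Working it through.** The documents state no expected rate for this analysis, so there is no figure to reproduce.

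**Number of post-baseline ALT/AST values, k.** The schedule has no liver tests at Month 1. In Months 2-18 they are "monthly (in months full serum chemistries not done"), with full chemistry in the other months: 17 values. Patients then "visit the clinic monthly for the first 18 months, followed by every 2 months"; Months 20, 22, ..., 60 give (60-20)/2 + 1 = 21 values. Follow-up adds 1. The maximum is 17 + 21 + 1 = 39. At the other end, nonresponders after 12 weeks "should be discontinued from the study, unless tangible clinical benefit from the use of fostamatinib is evident". They have k = 2 (Months 2 and 3), or 3 with follow-up. For patients already on fostamatinib in the prior study, the Day 1 sample might also count as post-baseline and add one; it is left out here.

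**Chance of at least one rise with no drug effect.** If baseline and the k later values are exchangeable and there are no ties, P = k/(k+1) and the expected number of rises is k/2. The last column is a simulation of 100,000 patients per setting. It assumes lognormal ALT with median 22 U/L, ULN 40, between-patient CV 35%, within-patient CV 10-30%, serial correlation 0-0.8, whole-unit rounding with ties not counted, and baseline ≤1.5x ULN.

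| Followed to | k | k/(k+1) | Expected rises, k/2 | Simulated P |
|---|---|---|---|---|
| Month 3 | 2 | 67% | 1 | 50-65% |
| Month 3 + follow-up | 3 | 75% | 1.5 | 58-74% |
| Month 12 | 11 | 92% | 5.5 | 80-91% |
| Month 18 | 17 | 94% | 8.5 | 86-94% |
| Month 60 | 38 | 97% | 19 | 93-98% |
| Month 60 + follow-up | 39 | 97.5% | 19.5 | not run |

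**Overall, under an assumed mix.** Some leave at Month 3 (k = 3) and the rest reach Month 18 (k = 17):
- 30% leave: 0.30 × 0.750 + 0.70 × 0.944 = 0.886
- 70% leave: 0.70 × 0.750 + 0.30 × 0.944 = 0.808

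**Room to show an effect** (k = 17, within-patient CV 20%, true 25% rise in ALT).
- Patient percentage: in the simulation it moves only from 92-93% to 99%.
- Mean events per patient: on the log scale the within-patient SD is √ln(1.04) = 0.198, so the SD of a difference is 0.198 × √2 = 0.280. P(a visit exceeds baseline) = Φ(ln 1.25/0.280) = Φ(0.223/0.280) = 0.79. The mean goes from 17/2 = 8.5 to about 13.4. With no effect at all, it goes from 1 at k = 2 to 19.5 at k = 39.

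**What a threshold count would look like.** In the same simulations, the no-effect rate of ALT ≥3x ULN is about 0-0.1% for k up to 38. Protocol Table 1 (rheumatoid arthritis studies) gives 38/723 = 5.3% and 37/710 = 5.2% on fostamatinib and 17/715 = 2.4% on placebo. Applied to 150 patients, these are about 8 cases (5.3%, 95% Clopper-Pearson CI 2.3-10.2%) and about 4 cases (2.7%, CI 0.7-6.7%). No Hy's law count can be projected, because the protocol gives no denominator for the five earlier cases.

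**The case against.** A reader might infer more than the documents support, in four ways.

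- **That nearly every patient, or about 95%, would be counted.** That fits patients followed for about 18 months or more. Those stopped at 12 weeks have only two or three values, and ties and serial correlation lower the figure further.
- **That the protocol's liver thresholds are never tabulated.** The shift tables give severity-graded patient counts for each analyte, and the bullets at issue are additions to them. The documents do not print the CTCAE cut-points, so whether a grade boundary falls at 3x or 5x ULN cannot be checked here. What can be said is that no visible SAP table names these multiples or the combination. SAP Appendix 14.1 is redacted, but its heading concerns exploratory efficacy and other endpoints; SAP 4.5, which lists the safety endpoints, is not redacted and has no such count.
- **That the SAP has settled on counting any rise.** It has not defined the event. SAP 4.5 frames laboratory changes by CTCAE grade, so graded increases may be meant. Either way, a definition is needed.
- **That both bullets are useless.** The mean number of events does respond to a drug effect. Its weakness is that it also follows the number of samples.

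It is also fair to say that Appendix 1 sets management triggers and does not prescribe tables. Potential Hy's law cases go to the Medical Monitor individually, and an independent safety review committee is in place. That reduces the risk that a case is missed, but it does not supply the count for the report. The AE tables depend on what investigators report as adverse events, so they do not supply it either.

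**Conclusion.** The concern holds in a limited form. The additional ALT/AST event is undefined. Read literally, the patient-level percentage would be about 50-75% for patients stopped near 12 weeks and 80-95% or more for those followed a year or longer, with no drug effect. Overall it would be about 81-89% under the assumed 30-70% leaving at Month 3. These figures rest on exchangeability, or on the simulation settings listed, and on that literal reading. The mean number of events largely reflects the number of samples unless it is given a denominator.

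Single-analyte severity is already covered by the CTCAE shift tables. The remaining gap is the protocol's explicit ULN multiples and, above all, ALT/AST and bilirubin elevation together, which tables of one analyte at a time cannot show.

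**What to change.** In SAP 11.2:

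1. Define the ALT/AST event by a threshold in place of any rise.
2. Express the event count per post-baseline sample or per patient-time.
3. Add counts and percentages of patients with on-treatment ALT or AST ≥3x ULN, ALT or AST >5x ULN, total bilirubin >2x ULN, and the Appendix 1 combination (ALT/AST ≥3x ULN with total bilirubin >2x ULN and ALP <2x ULN). State what counts as concurrent; the scheduled liver panel contains all four tests, so a same-sample rule is workable.
4. Use scheduled and unscheduled samples. Appendix 1 generates repeat tests every 72 hours, and SAP 11.3 already uses both kinds of visit for maximum and last blood pressure.

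Keep the CTCAE shift tables. The format has precedents in SAP 11.3, which counts patients at explicit blood pressure cut-offs, and in Protocol Table 1, which reports ALT/AST ≥3x ULN. This is a cheap improvement: the only cost is revised SAP wording and one small additional table from data already collected.
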